### 9.2 Populations for Analyses

**The subject population** As further detailed in the inclusion and exclusion criteria will consist of consecutive consenting lupus patients between ages 18 and 70 who have active polyarticular arthritis characterized by 3 or more tender and 3 or more swollen joints at the screening visit meeting the BILAG 2004 criteria for  $\geq$  B disease (+/- additional evidence of disease activity in other organs).

**The clinical justification** is based on the combination of unmet need in treating a significant, potentially disabling illness, while ensuring a healthy enough population to justify the risks of studying a biologic treatment vs placebo.

**Power Analysis:** Chi Sq or the Fisher's exact test will be used for analysis. The table below has been powered on the assumption that the placebo group will have a result similar to (or even a bit more responsive than) that found in the BOLD study (which was the test prototype for this protocol to determine the safety and feasibility of the statistical assumptions for the placebo study). Data from the BOLD study confirm that there should be a near zero (2.4%) percent response by BICLA at six months in the placebo group in a study with background IS withdrawal. Therefore our assumption of at least 5% response in the placebo group in an identical trial design is reasonable. The second assumption is that the treatment group will have a response rate somewhere between those found in the epratuzumab (by BICLA) and BLISS phase II/III (by SRI) biologic studies e.g. a predicted response rate between 35 and 50%. The most important basis for this assumption, however are the data from patients with lupus arthritis in the Phase II abatacept study, where physicians rated 40% of

the patients treated with abatacept as having “no flare” after baseline. Therefore this expected range by BICLA seems reasonable. (please see power analysis table below which is based on powering the primary endpoint at a range of expected response rates in treatment and placebo groups with a sample size of 60 patients, alpha=0.05).

#### **Power of 60 patient study if alpha=0.05 with response rates:**

	Rate 1	Rate 2	Rate 3	Rate 4	Rate 5	Rate 6	Rate 7
abatacept	60%	55%	50%	45%	40%	35%	35%
placebo	20%	15%	10%	10%	5%	5%	3%
power	0.84	0.86	0.89	0.80	0.86	0.77	0.84

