Statistics:	
Primary Clinical Endpoint: proportion of patients on abatacept vs placebo who meet BICLA criteria at month 6 compared to baseline by Ch sq or Fishers Exact Test. Powering of the Study Based on the Primary Endpoint: Powering assumptions assume response rates ranging from 35-50%. based on data from patients with lupus arthritis in the Phase II abatacept study, where physicians rated 40% of the patients treated with abatacept as having “no flare.” Using the BICLA, response rates in the epratuzumab EMBLEM trial was also about 40% at optimal dosing, therefore this range seems applicable. Data from the BOLD study confirm that there should be a near zero (2.4%) percent response by BICLA at six months in the placebo group in a study with background IS withdrawal. Therefore our assumption of at least 5% response in the placebo group in an identical trial design is reasonable and with range of 40-50% response in the treatment group power > 0.8 to detect a difference. Exploratory Analysis of Primary Endpoint: To address potential confounders in a small study a propensity score will be applied to simplify multiple variables into one variable.
 
Secondary Clinical Endpoints: BICLA and SRI at each month. Mean SLEDAI, BILAG, CLASI, PGA, DIAL and PRO by paired T test. Main Biologic Endpoint: Patients who do or do not exhibit proposed relative differences in the ratio of IL6/IL23/IL17 to Foxp3/TGF<math>\beta</math> (suggesting T Cell signaling imbalance) or aberrant ErK phosphorylation (indicating abnormal signaling through B Cell receptor) at baseline will be compared for proportion of responders in treatment vs placebo group. Patients identified at baseline with high TH17 signal or ErK phosphorylation with <math>\geq</math> 50% change towards healthy mean (+2SD) after treatment will be compared separately for response rates. These endpoints will be described in terms of confidence intervals based on the primary clinical endpoint. Analysis of Secondary and Exploratory Biologic Endpoints will include mean (or median) change in cytokine, immunoglobulin and gene expression levels explored based on known patterns of overexpression in SLE. Bucketing of baseline profiles might be used to develop propensity scores suitable for a simplified refinement of the primary biologic endpoint by combining variables that might either increase or decrease the likelihood of response. Given the complex array of data we are likely to generate, principal component analysis can be applied to these exploratory studies to identify directions (principal components) along which the variation of the data is maximal.

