No targeted therapy can be expected to work for all patients in a disease with such heterogenous underlying biology. There is thus an inevitable low ceiling on the percentage of patients likely to respond if they are entered into a trial without biology-based pre-qualification steps. Although the current trial is designed to maximize effect size between treatment and placebo there is little that can be done to increase the inevitable 50% limit on response rates of targeted biologics, regardless of the discriminatory capacity of the endpoints. For this reason, biomarker discovery to provide a more meaningful basis for selecting patients for targeted treatments should be a high priority both for optimizing patient care and for the appropriate dissemination of treatments that are not “first to market.” As more biologic treatments enter the field, strategic biomarker-based matching of treatments and individual patients may help to ensure a competitive effect size, gain faster approval at less expense, gain more rapid penetration and retention of the optimal (and medically most appropriate) market, and convince third party payers of the utility of a treatment.

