The study population will include patients between the ages of 18 and 70 who meet a minimum of 4 1997 revised ACR criteria for SLE and who present with a minimum of 3 tender and 3 swollen joints attributable to lupus arthritis. Patients may have other active manifestations of SLE, and, in the opinion of the investigator, they must be sick enough for intention to treat with a biologic and stable enough for this trial design, which includes withdrawal of any background immune suppressants, to be appropriate.

This study will enroll patients until 60 have completed the protocol through at least the six month point. Randomization will be 1:1 to abatacept or placebo. Approximately 30 patients are expected to complete each arm. At each visit history, physical, and blood tests appropriate to complete the outcome measures will be performed, and adverse event reporting and medication updates will be performed.

Subjects may continue to take nonsteroidal anti-inflammatory medications (including *prn* NSAIDS) and up to 20 mg prednisone (or oral steroid equivalent) daily during the study although steroids will be tapered as tolerated. If the patient is taking an immune suppressant (e.g. antimalarials, mycophenolate mofetil, azathioprine, leflunomide, methotrexate, a calcineurin inhibitor or belimumab) at screening, this must be stopped prior to or on the day of the baseline visit. Patients can elect to receive one or more depomedrol injection(s) up to a total of 320 mg total at the time of the screening visit and/or up to and including the Month 2 visit. Daily oral steroids will be tapered as tolerated if and when the patient begins to improve.

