## 9. Statistical Considerations

**Enrollment is expected to include at least 70 screened and 60 randomized subjects** subjects have either reached a six month endpoint and/or been defined as a permanent non-responder for off protocol treatment or by dropping out of the protocol.

**The primary endpoint is the proportion of placebo vs treatment subjects who meet the primary endpoint of BICLA response using Chi Square analysis at month 6 as determined by an intent to treat analysis**

Subjects who drop out prematurely for any reason or are treated with off protocol medications or cross over to open label for lack of response at Month 3-6 are considered non responders at month 6.

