### 9.1 Sample Size Determination

**Sample Size** Based on data from the BOLD study confirming the low response rates in a placebo group at 6 months in a study design identical to the structure of this protocol (1/41 patients or 2.4% met the BICLA response at 6 months in that study) and based on the assumption that the response rate to abatacept using this design and these endpoints would be at least equivalent to what was found in the Phase II Epratuzumab or Phase III BLISS studies (roughly 40-50% response). The sample size was optimized at 60 patients in a 1:1 randomization scheme with alpha = 0.5 and desired power 0.8.

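### The power table states no method, fits neither test the plan allows, and omits the pairs of 35-40% abatacept with 10% placebo, where power falls below the 0.8 target

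*Combined protocol and SAP*

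**What the plan says.** Section 9 makes the primary comparison "BICLA response using Chi Square analysis at month 6 as determined by an intent to treat analysis". Section 9.2, in the paragraph that introduces the power table, is less definite: "Chi Sq or the Fisher's exact test will be used for analysis". The synopsis (Statistics) also allows either test. No section says whether chi-square carries a continuity correction.

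For the rates, the synopsis and 9.2 predict 35-50% response on abatacept. They take the BOLD result of 1/41 (2.4%) for placebo and add a margin: "our assumption of at least 5% response in the placebo group in an identical trial design is reasonable". Section 9.2 presents the tabulated rates as those expected in the two groups. The table is headed "Power of 60 patient study if alpha=0.05 with response rates" and prints (abatacept/placebo: power) 60/20: 0.84; 55/15: 0.86; 50/10: 0.89; 45/10: 0.80; 40/5: 0.86; 35/5: 0.77; 35/3: 0.84. The target power in 9.1 is 0.8.

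**The concern.** A power figure has meaning only for a stated test. Here the test is left open and the table's method is not given, so a reader cannot tell which analysis the figures describe. The choice can decide the result: 8/30 against 2/30 is significant by uncorrected chi-square but not by Fisher.

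The layout has a larger consequence. In the table, 10% placebo is paired only with 45% and 50% abatacept, 15% only with 55%, and 20% only with 60%. The last two abatacept rates lie above the plan's own 35-50% range. Across these columns power looks nearly flat. Section 9.2 gives most weight to a 40% response seen with abatacept in the Phase II arthritis patients, and the synopsis cites about 40% from the epratuzumab trial. The table shows 40% against 5% placebo only. A sponsor using this trial for a go/no-go decision cannot see what happens at 40% if placebo response reaches 10%.

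**Working it through.** **Inputs.** 30 per arm (60 patients, 1:1; Section 4.1: "Approximately 30 patients are expected to complete each arm"). Alpha 0.05 from the table heading, taken as two-sided because sidedness is not stated. Section 9.1 prints alpha as 0.5, which looks like a misprint and was not used. Dropouts count as non-responders, so N is not reduced.

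**Step 1: reproduce the printed figures.** With p̄ = (p1 + p2)/2, the continuity-corrected approximation is

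power = Φ{ [ |p1 − p2| − 1/n − 1.96·√(2p̄(1 − p̄)/n) ] / √[ (p1(1 − p1) + p2(1 − p2))/n ] }.

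For 40 against 5: p̄ = 0.225; numerator 0.35 − 0.0333 − 1.96 × 0.1078 = 0.1053; denominator √(0.2875/30) = 0.0979; Φ(1.076) = 0.859, printed 0.86.

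**Step 2: exact power.** Sum the binomial probabilities Bin(x; 30, p1) × Bin(y; 30, p2) over all tables (x, y) that the test rejects.

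| Abatacept/placebo (%) | Printed | Corrected approx. | Exact uncorrected chi-square | Exact Fisher |
|---|---|---|---|---|
| 60/20 | 0.84 | 0.848 | 0.905 | 0.851 |
| 55/15 | 0.86 | 0.869 | 0.922 | 0.876 |
| 50/10 | 0.89 | 0.897 | 0.949 | 0.914 |
| 45/10 | 0.80 | 0.804 | 0.891 | 0.830 |
| 40/5 | 0.86 | 0.859 | 0.943 | 0.893 |
| 35/5 | 0.77 | 0.749 | 0.880 | 0.788 |
| 35/3 | 0.84 | 0.830 | 0.946 | 0.875 |

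The corrected approximation is within 0.01 of print in six columns and 0.021 off at 35/5. Exact chi-square exceeds print by 0.059 (50/10) to 0.110 (35/5), exact Fisher by 0.011 (60/20) to 0.035 (35/3). At 30 per arm, Yates-corrected chi-square and two-sided Fisher reject exactly the same tables, so the Fisher column also covers a corrected chi-square.

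**Step 3: does the choice of test matter?** For 8/30 against 2/30, z = 0.20/√(2 × (1/6)(5/6)/30) = 2.08, p = 0.038 by uncorrected chi-square; Fisher gives p = 0.080.

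**Step 4: the full grid inside 35-50% abatacept** (exact chi-square / exact Fisher, same enumeration):

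| Placebo | 35% | 40% | 45% | 50% |
|---|---|---|---|---|
| 3% | 0.946 / 0.875 | 0.978 / 0.946 | 0.992 / 0.980 | 0.998 / 0.994 |
| 5% | 0.880 / 0.788 | 0.943 / 0.893 | 0.977 / 0.953 | 0.992 / 0.982 |
| 10% | 0.661 / 0.545 | 0.796 / 0.705 | 0.891 / 0.830 | 0.949 / 0.914 |
| 13% | 0.523 / 0.409 | 0.679 / 0.575 | 0.806 / 0.724 | 0.895 / 0.839 |

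At 40% abatacept, moving placebo from 5% to 10% costs 0.943 − 0.796 = 0.147 by chi-square and 0.893 − 0.705 = 0.188 by Fisher.

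**Step 5: is 10% placebo plausible on the plan's own data?** The exact (Clopper-Pearson) 95% interval for 1/41 is 0.06% to 12.9%. The chance of one or fewer responders in 41 at a true rate of 10% is 0.074, so the data do not exclude it.

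**The case against.** The strongest reply is that the table is cautious. Fisher is allowed in the same paragraph that introduces it, a continuity-corrected formula approximates Fisher, and the gap to exact Fisher is at most 0.035. Section 9 does not say that its chi-square is uncorrected. All seven figures err on the low side. This stands: the table inflates nothing, and the gap of up to 0.11 applies only if chi-square means the uncorrected test.

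The reply also holds that the table does show sensitivity to placebo. Its last two columns hold abatacept at 35% while placebo moves between 3% and 5%, and power falls from 0.84 to a disclosed 0.77. This stands too. A reader might infer that the abatacept rate rises every time the placebo rate rises, or that weak pairs are concealed at the planning value of 5%. The table supports neither: at 5% placebo the only printed or omitted pair in the 35-50% range below 0.80 by Fisher is 35/5, and it is shown.

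Finally, the 5% may be meant only as a margin above 2.4%, with 10-20% as sensitivity cases. This does not answer the point. Section 9.2 calls the tabulated rates expected, and a sensitivity case that comes with a higher treatment rate does not test sensitivity.

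**Conclusion.** The point holds as one of method and presentation. The table's method is unstated, and its figures match the exact power of neither permitted test: 0.06-0.11 low for uncorrected chi-square, 0.01-0.035 low for Fisher. Above 5% placebo it shows only abatacept rates of 45% or more. It therefore omits 40 against 10 (0.80 by chi-square, 0.796 before rounding; 0.71 by Fisher) and 35 against 10 (0.66; 0.55).

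A reader might go further and conclude that the trial is under-powered as planned. The documents do not support that: at 40-50% against 5%, power exceeds 0.8 by every calculation here, the lowest being 0.859 at 40/5. Nor are the 55% and 60% columns errors in themselves. The introduction's "inevitable 50% limit on response rates of targeted biologics" is argument rather than a design parameter. The difficulty is that those columns are the only ones carrying 15-20% placebo.

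The figures assume 30 per arm, two-sided alpha 0.05 and independent binomial responses.

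**What to change.** Name one primary test in Section 9, 9.2 and the synopsis, and say whether chi-square is corrected. Recompute the table exactly for that test and state the method and sidedness beneath it. Print a grid of abatacept 35, 40, 45 and 50% by placebo 3, 5, 10 and 13% (the last being the upper limit for 1/41, rounded), with the interval 0.06-12.9% beside the placebo assumption. Carry the same figures into the synopsis and 9.1, and reconcile the alpha printed in 9.1 with the 0.05 in 9.2. Whether to keep the 55% and 60% columns as extra cases is a matter of preference.

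The cost is one table and a few sentences, with no change in N. The downside for the sponsor is that, although the printed pairs rise, the new cells at 35% and 40% abatacept with 10% or 13% placebo fall below 0.80 (40/10 only marginally by chi-square), as does 45/13 if Fisher is chosen.

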### **9.3 Endpoint Definitions:**

#### **9.3.1 Primary endpoint (and how it tests the study hypothesis)**

The primary endpoint is to compare the response rates of abatacept treated to placebo treated patients which addresses the main study hypothesis by specifically testing the efficacy of abatacept in lupus patients with active arthritis at baseline who complete a protocol designed with withdrawal of confounding background medications using a robust endpoint that has shown the ability to discriminate between effective treatment and placebo.

#### **9.3.2 Secondary and Exploratory Endpoint Definitions** (see specific descriptions of endpoints in 6.41 and 6.42, below some further discussion of the analysis plan

### **9.4 Analyses To Be Performed**

#### **9.4.1 Demographics and Baseline Characteristics**

The demographics of the patients who are likely to participate in this study should be reflective of the Oklahoma Lupus Cohort which will be the source for most of our recruitment activity. The age range of participants in this study will be between 18 and 70, and based on our experience with interventional trials requiring significant disease activity, we expect the majority of subjects to be within the ages of 25 and 55. There is no stratification scheme to be imposed based on demographics and baseline characteristics, but variables of age, race, gender, steroid use, autoantibody positivity, complement consumption, and BILAG score at baseline will be described in order to identify any glaring imbalances in group assignments..

#### **9.4.2 Safety Analyses**

In a study this size, and based on data from earlier trials of abatacept in RA and SLE it is unlikely that statistically significant differences will be found in overall AEs, SAEs or AEs of special interest. Safety Analyses will be descriptive in nature and complete in their presentation, following the examples of the earlier lupus and RA safety reports.

#### **9.4.3 Efficacy Analysis**

**Primary Endpoint:** The primary analysis upon which this study is powered will be a two by two analysis of response rates to BICLA endpoint in treatment vs placebo group.

**Exploratory Analysis of Primary Endpoint:** To address potential confounders in a small study a propensity score will be applied to simplify multiple variables into one variable.

**Analysis of Secondary Clinical Endpoints:** include the BICLA and SRI response performed at each month using a Chi Square approach as well as mean SLEDAI, BILAG, CLASI, PGA, DIAL and PRO by paired T test comparing baseline to endpoint (EOS or each month) in placebo patients and separately in abatacept treated patients.

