## 2. STUDY OBJECTIVES

**2.1 Primary Objective:** To compare response rates between Abatacept-Treated and Placebo-Treated Patients with active lupus arthritis in a trial designed with background immune suppressant

withdrawal, limited steroid rescue, and a robust, discriminatory endpoint. Statistical powering is based on this primary objective.

**2.2 Secondary Objectives:** Secondary clinical endpoints will include: SRI 4/5, changes in joint counts, SLEDAI, BILAG, CLASI, PGA, and DIAL measures. We will also Integrate biologic discovery into the clinical trial to support both pre-specified and exploratory biomarker discovery. Data will be generated that might be used to help select more appropriate patient subsets for future trials and to guide optimal dosing strategies. Optimizing patient selection and dosing are important goals for further increasing demonstrable effect size in trials by increasing the response rates in the treatment group.

Optimizing patient selection and dosing are important goals for further increasing effect size in trials. In fact, the two Aims of this project are co-dependent, since each increases the likelihood of interpretable data and could have high impact on increased effect size for an effective product. Also, Aim 2 would be less feasible without the strategy of Aim 1 to decrease the cacophony of background medications, which have clouded interpretation of many treatments for SLE in the past.

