## **Ethical Considerations:**

Integration of biologic discovery into clinical trials will generate data that might be used to help select more appropriate patient subsets for future trials and future treatment in clinic and to guide optimal dosing strategies. This is an ethical consideration since it could decrease the numbers of patients inappropriately exposed to a study medication in trials and in practice, and by allowing a better delineation of efficacy in the right population(s) this could also decrease the likelihood of widespread exposure in Phase III trials prior to acquiring sufficient data supporting potential efficacy.

The ethical basis of the current trial design has been debated widely in the lupus community. There is a realistic concern that withdrawal of background therapy will increase the risk of lupus flares and this trial design would be inappropriate for very ill patients such as those with active nephritis. However by decreasing the continued use of background immune suppressants which were obviously not working at the time of entry, by allowing steroid rescue and even restarting of meds as needed during the trial (defining such patients as non-responders) this design could be argued to be far more ethical than trials which legislate continuance of inadequate and potentially toxic background immune suppressant treatments for an entire year, with probable increase in risk for infections. In such protocols, patients who do not improve have only the choice of minimal rescue steroids or to drop out of the study, leading to unnecessary suffering which will not be required in this trial design. Finally, the concern about increasing flare risk should be somewhat alleviated by the results of the MMF, BOLD and Rontalizumab studies (all three of which have been completed using this trial design, and the latter presented at ACR 2012 (39)

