### **6.3.1 Physical Examinations**

Physical examinations will be performed at every visit, suitable to assess patient safety and to perform the efficacy evaluations which are multisystem indices (see below)

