## **6.4.2 Secondary Efficacy Assessments**

***All of the individual components of the BICLA will be assessed in different ways as secondary endpoints. These will include:***

1. BICLA response at each month
2. SRI 4 and 5: Response is defined at an endpoint date (EOS and each month vs baseline) The SRI endpoint (7) is defined as a 4 (or 5) point drop in SLEDAI compared to baseline without an increase in BILAG or 10% worsening by PGA.
3. Tender and swollen joint counts (to be analyzed separately and as composite score)
4. Change in SLEDAI scores (EOS and each month vs baseline)
5. Change in PGA scores (EOS and each month vs baseline)
6. Change in BILAG numerical scores (Addition of organ scores where each A=12, B=8, C=1 and D or E=0).
7. Musculoskeletal BILAG response (% with one grade drop and % who reach C or lower)
8. Responder Analysis using the primary endpoint and assessing baseline evidence of (and changes in) a panel of markers selected to identify high levels of IL6/TH17 signalling, and/or B Cell signaling (Erk/Blys). All methods proposed have been previously standardized and are currently available in our laboratory as reviewed above. These will be re-standardized for the current study.

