## Exploratory Clinical Assessments

Exploratory clinical endpoints will include:

Changes in CLASI, (cutaneous lupus endpoint)

LFA REAL (Rapid, Evaluation of Activity in Lupus)

Patient-reported outcomes: (LUPUS PRO and SF-36 domains)

These analyses will be performed according to the training on the LFA POINT website (Lupus Foundation of America Professional Online Instrument Training) which all investigators will be required to use for certification.

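### Continuous secondary endpoints are tested within each arm by paired t-test, with no planned abatacept-versus-placebo difference

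*Combined protocol and SAP*

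**What the plan says.** For the means of SLEDAI, PGA, BILAG, CLASI, DIAL and PRO, Section 9.4.3 specifies the analysis "by paired T test comparing baseline to endpoint (EOS or each month) in placebo patients and separately in abatacept treated patients". The synopsis (Statistics) is shorter and names no comparator: "Mean SLEDAI, BILAG, CLASI, PGA, DIAL and PRO by paired T test".

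Section 6.4.2 defines the SLEDAI and PGA endpoints as change against baseline. It lists "Tender and swollen joint counts (to be analyzed separately and as composite score") and "Musculoskeletal BILAG response (% with one grade drop and % who reach C or lower") without naming a test for either. The clinical between-arm comparisons that are planned all concern binary response: BICLA at Month 6, BICLA and SRI by month with a chi-square approach, and responder proportions within biomarker subsets (Section 9.4.4).

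The tier of several measures is inconsistent. Section 2.2 states "Secondary clinical endpoints will include: SRI 4/5, changes in joint counts, SLEDAI, BILAG, CLASI, PGA, and DIAL measures". Section 4.1 and the synopsis also treat CLASI and the patient-reported outcomes as secondary. The list under Exploratory Clinical Assessments opens "Exploratory clinical endpoints will include" and then names CLASI, LFA REAL, LupusPRO and SF-36. The section on optional exploratory analyses gives the patient-reported outcomes a further, separate exploratory role.

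**The concern.** A within-arm p-value reflects change from any cause. The protocol itself supplies causes common to both arms: entry on active arthritis (regression to the mean), depomedrol injections allowed in both arms through Month 2 (Section 4.1), and worsening once background drugs stop. On the last, the ethics section says "There is a realistic concern that withdrawal of background therapy will increase the risk of lupus flares".

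For each measure the plan therefore yields two separate p-values and no estimate of benefit over placebo. Comparing one p-value with the other can suggest a benefit that is absent or hide one that is real. The arm means will exist, so a difference could be computed later, but the model, the interval and the handling of patients who switch to open-label abatacept would then be chosen after the data are seen. Section 1.6 says the trial should support a go/no-go decision, and Section 9.4.4 contemplates continuing development without significance on the primary endpoint. Supportive measures would plausibly be weighed in that situation.

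**Working it through.** **The plan's own figures.** The only power figures are for binary BICLA response (Section 9.2). For 40% versus 5%, 30 per arm and two-sided alpha 0.05, the continuity-corrected formula gives pooled rate 0.225, null SE √(2×0.225×0.775/30) = 0.108 and alternative SE √((0.24+0.0475)/30) = 0.098. Power is Φ((0.35 − 1/30 − 1.96×0.108)/0.098) ≈ 0.86, as stated. This confirms n and alpha for what follows; it does not bear on the continuous endpoints, for which the plan states nothing.

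**Inputs.** About 30 completers per arm (Section 4.1); alpha 0.05 (power table), two-sided assumed. The SD of change and the expected mean change are not given, so results are in units of the SD of change, with + meaning improvement.

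**No drug effect, shared change d.** The paired t statistic in each arm has 29 df, critical value 2.045 and noncentrality d√30. Let p be the chance that one arm is significantly improved. The arms are independent, so the chance of abatacept improved and placebo not is p(1−p).

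| d (SD) | p | Abatacept improved, placebo not |
|---|---|---|
| −0.2 | 0.001 | 0.1% |
| −0.1 | 0.006 | 0.6% |
| 0 | 0.025 | 2.4% |
| +0.2 | 0.184 | 15% |
| +0.37 | 0.500 | 25% (maximum) |
| +0.5 | 0.754 | 19% |
| +0.8 | 0.989 | 1% |

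By symmetry, if both arms worsen, the pattern of placebo significantly worse and abatacept not appears in 7%, 15%, 25%, 19% and 1% of trials at −0.1, −0.2, −0.37, −0.5 and −0.8 SD. In 20,000 simulated trials per setting (baseline-to-follow-up correlation 0.5), these patterns were reproduced and a between-arm ANCOVA rejected in 4.7% to 5.2% throughout.

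**True extra 0.5 SD on abatacept.** The chance that both arms are significant is the product of the two arms' p.

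| Placebo change (SD) | Both significant | Abatacept only | ANCOVA significant, given both significant |
|---|---|---|---|
| 0.3 | 35% | 64% | 27-43% |
| 0.5 | 75% | 25% | 44-58% |
| 0.8 | 99% | 1% | 53-64% |

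The last column is simulated; its range is for assumed correlation 0.7 to 0.3.

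**Precision of a between-arm analysis.** The ANCOVA residual SD is √((1+ρ)/2) in SD of change: 0.806, 0.866 and 0.922 at ρ = 0.3, 0.5 and 0.7.

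| 30 per arm | Unadjusted | ANCOVA, ρ = 0.3 / 0.5 / 0.7 |
|---|---|---|
| Power for 0.5 SD | 48% | 66% / 59% / 54% |
| Detectable at 80% power (SD) | 0.74 | 0.59 / 0.64 / 0.68 |
| 95% CI half-width (SD) | 0.52 | 0.42 / 0.45 / 0.48 |

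**Why a switch rule matters.** Start from a true 0.736 SD (unadjusted power 80%) and use values as randomised. If a fraction f of placebo patients switch and gain a fraction g of the effect, the Month 6 difference is 0.736(1−fg). With g = 0.5 it is 0.66 SD at f = 20% and 0.55 SD at f = 50% (power 71% and 56%). With g = 1 it is 0.59 and 0.37 SD (power 61% and 29%). If values after a switch are instead set to missing and, say, 24 abatacept and 15 placebo values remain (assumed), ANCOVA power for 0.5 SD falls from 54-66% to about 36-45%.

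**The case against.** The strongest reply is that little depends on these tests. The trial is sized on BICLA alone, Section 9.4.4 ties continued development to the effect size in the primary endpoint, and no section says that one arm's p-value should be read against the other's. The 25% is the worst case on an assumed scale; at zero or large shared change it is 1% to 2%. All of this is true and limits the stakes. It does not supply a comparison: the plan offers no other way to use these means as evidence on abatacept.

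Nor is a between-arm test always more sensitive. When placebo improves by 0.3 SD and abatacept adds 0.5 SD, the abatacept-only pattern appears in 64% of trials, while ANCOVA detects the difference in 54-66%. But that same pattern appears in 23% of trials with no drug effect, so its apparent sensitivity comes without error control.

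Three further points stand as additions. Setting values to missing after a switch costs power, as shown above. BILAG numerical scores (12, 8, 1, 0) and CLASI, where skin disease is not required for entry, may be far from normal, and the simulations assume normal data with equal variances. Finally, the missing joint-count form field is weak evidence, because the appendices supplied also lack CLASI, DIAL and patient questionnaire forms.

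**Conclusion.** The concern holds and should be fixed. Section 9.4.3 states the within-arm rule explicitly, so this is a chosen analysis rather than an omitted detail, and no other section supplies the randomised contrast for a continuous clinical endpoint. Under no drug effect, a one-arm-only pattern favouring abatacept can reach 25%, against about 5% two-sided for a between-arm test. With a real 0.5 SD benefit, both arms are significant in 35% to 99% of trials as placebo improvement goes from 0.3 to 0.8 SD. These figures rest on 30 complete values per arm, normal data, two-sided 0.05 and assumed changes in SD units. The primary BICLA analysis and the monthly BICLA and SRI comparisons are not affected.

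**What to change.** - For Months 1-6, replace the paired tests with a baseline-adjusted between-arm mean difference and 95% CI. Use either ANCOVA (outcome on arm and baseline) or one repeated-measures model with arm, visit, arm-by-visit and baseline; name one in advance. State an alternative, such as a rank-based analysis, for markedly skewed or zero-heavy scales.
- Apply the same to joint counts, and name a between-arm test for the musculoskeletal BILAG response.
- Pre-specify how missing values and values after open-label switch or off-protocol treatment enter these analyses. The non-responder rule in Section 9 works only for binary response. As-randomised and set-to-missing are both defensible: make one the main analysis and the other a sensitivity analysis. The rule must run from the first dose, because Section 5.6.1 allows immune suppressants to restart before Month 3.
- Label each measure secondary or exploratory after reconciling the synopsis, Sections 2.2, 4.1, 6.4.2 and 9.4.3, and the two exploratory-assessment sections. State that multiplicity is not controlled.
- Keep within-arm changes, and all Months 7-12 summaries (no placebo control by then), descriptive and without p-values.

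The cost is a text amendment prepared with BMS and approved by the IRB (Section 10.1.1). SLEDAI, PGA, BILAG, CLASI, DIAL and the questionnaires are already collected at baseline and monthly. Joint counts have no row in the Time and Events Schedule. They could come from the monthly examination (Section 6.3.1: "Physical examinations will be performed at every visit, suitable to assess patient safety and to perform the efficacy evaluations"), but a schedule row and form field may be needed. The price is visible imprecision: even with complete data, a true 0.5 SD effect would be missed in about 34% to 46% of trials with ANCOVA.
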